25.2.3.2.5 EQ-5D-5L

25.2.3.2.5.1 Derivation

EQ-5D-5L is collected at baseline and day 30, 60, 90, 120 and 180. The total health score today is

collected and ranges from 0 to 100. A patient will also classify their health on the day of completion

for the following: Mobility, Self-care, Usual activities, Pain/Discomfort and Anxiety/Depression which

have the following categorisations of problems/pain/anxiety/depression: no, slight, moderate, severe

and unable/extreme.

Change from baseline for total health score will be calculated at day 120 and day 180 as:

Day 120 – baseline and day 180 – baseline.

25.2.3.2.5.2 Analysis

The number of patients to complete the EQ-5D-5L at each timepoint will be reported. Summaries will

be provided as in 25.2.3.2.2.2, with day 180 and change from baseline to day 180 also provided.

Continuous summaries will also be provided for scores at day 30, 60 and 90. Profile plots will also be

provided from baseline to day 180.

CLINICAL TRIALS CENTRE LCTC

25.2.3.2.6 PHQ-9

25.2.3.2.6.1 Derivation

PHQ-9 is collected at baseline and days 30, 60, 90 and 120. A total of 9 questions are responded to in

regards to how often a participant is bothered by the problems over the last 2 weeks. These are scored

as "Not at all" (0), Several days (1), More than half the days (2) and Nearly every day (3). The scores

are then summed to create a total score.

The change from baseline total score will be calculated as the day 120 score – baseline score.

25.2.3.2.6.2 Analysis

The number of patients to complete the PHQ-9 at each timepoint will be reported. Summaries will be

provided as in 25.2.3.2.2.2. Continuous summaries will also be provided for scores at day 30, 60 and

90. Profile plots will also be provided from baseline to day 120.

25.2.3.2.7 BPI

25.2.3.2.7.1 Derivation

BPI is collected at baseline and days 30, 60, 90 and 120. A total of 9 questions are responded to in

regards to the pain experienced by each participant, questions 1,2, 7 and 8 will not be summarised.

Questions 3 to 6 summarise the pain experienced by the participant:

• At its worst in the last 24 hours

• At its least in the last 24 hours

On average

Right now

Each category is score 0 to 10 as 'No pain' to 'Pain as bad as you can imagine'.

Question 9 ask patients how, in the last 24 hours, pain interferes with:

General activity

Mood

Walking ability

Normal work (includes both work outside the home and housework)

Relations with other people

Sleep

Enjoyment of life

LCTC\_ST003\_TEMP1: SAP Template, V0.1, 08/01/2021 (developed using LCTC\_GE001\_TEMP4: LCTC Template of a Template, V1.0, 04/09/2020)

LIVERPOOL CLINICAL TRIALS CENTRE LCTC

Each category is score 0 to 10 as 'Does not interfere' to 'Completely interferes'. For question 9, the

average pain interference score will be calculated using the mean of the 7 categories responded to.

25.2.3.2.7.2 Analysis

The number of patients to complete the BPI form at each timepoint will be reported. Summaries will

be provided as in 25.2.3.2.2.2 for questions 3 to 6 and for the average pain interference score for

question 9. Continuous summaries will also be provided for scores at day 30, 60 and 90. Profile plots

will also be provided from baseline to day 120 for continuous data.

25.2.3.2.8 HADS

25.2.3.2.8.1 Derivation

The HADS questionnaire is completed at baseline and day 30, 60, 90 and 120. The questionnaire

contains 7 anxiety and 7 depressions questions which answers are ranked 0 to 3 based on how the

patient has felt the past week. The total anxiety and depression scores are calculated from the 7

responses and ranges from 0 to 21.

The change in score from baseline will be calculated as day 120 minus baseline score for both total

anxiety and total depression score.

25.2.3.2.8.2 Analysis

The number of patients to complete the HADS form at each timepoint will be reported. Summaries

will be provided as in 25.2.3.2.2.2 for anxiety and depression separately. Continuous summaries will

also be provided for scores at day 30, 60 and 90. Profile plots will also be provided from baseline to

day 120.

25.2.3.2.9 Skin sensitivity by mechanical QST.

Analysis to be performed by the Co-I.

25.2.3.2.10 Limb volume

25.2.3.2.10.1 Derivation

Limb volume is collected at Screening, day 60 and day 120 for both Upper and Lower Limb measured

in cm. Change in limb volume will be summarised as volume at day 120 minus screening.

LCTC\_ST003\_TEMP1: SAP Template, V0.1, 08/01/2021 (developed using LCTC\_GE001\_TEMP4: LCTC Template of a Template, V1.0, 04/09/2020)

CLINICAL TRIALS CENTRE LCTC

25.2.3.2.10.2 Analysis

Summaries will be provided as in 25.2.3.2.2.2 for upper and lower limb volume separately. A

continuous summary of limb volume at day 60 will also be provided.

25.2.3.2.11 Work status

25.2.3.2.11.1 Derivation

Work status is recorded at baseline and day 120, with the following categories:

Employed

Self-employed

Not working.

25.2.3.2.11.2 Analysis

Categorical data will be summarised using frequencies and percentages at baseline and day 120 with

the denominator being those who completed the question at each timepoint.

To compare work status at baseline and day 120 a cross-tabulation will be provided with two

percentages using the denominators of total number of patients in the work status category at

baseline and at day 120 i.e. row and column percentages. A simiplified table of working (classified as

employed or self-employed) and not working at baseline and day 120 will also be provided.

26 Safety Evaluations

All non-serious adverse events (AEs) and SAEs reported by the clinical investigator will be presented

in a table (or non-serious adverse reactions (ARs) and SARs if the study does not capture unrelated

AEs). The number (and percentage) of patients experiencing each AE/SAE will be categorised by

severity (mild, moderate, severe). For each patient, only the maximum severity experienced of each

type of AE will be displayed. The number (and percentage) of occurrences of each AE/SAE will be

presented. No formal statistical testing will be undertaken.

27 Additional Analyses

No additional analysis planned.

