5.3.1 Potential Risks

As Anakinra is currently used for treating autoimmune diseases it has a well-established side effect profile. There are not expected to be any specific side effects that relate to refractory moderate to severe CRPS with the exception of possible increases in pain, and new pain at the subcutaneous injection side. The latter is a relevant potential risk as CRPS is a post-traumatic condition and an injection constitues a very minor trauma; this risk will be carefully monitored. Injection sites will be rotated to minimise this risk. Of note, in the CRPS literature there are to our knowledge no reports about development of new CRPS at subcutaneous injection sites in patients with established refractory CRPS.

Anakinra can cause ARs such as:

- 1. Worsening of CRPS symptoms (presumed risk)
- 2. New CRPS symptoms at the IV injection site (presumed risk)
- 3. Nausea, vomiting, diarrhoea and abdominal pain (10%)
- 4. Headache (12%)
- 5. Joint pain (0-12%)
- 6. Flu like symptoms
- 7. Infection, bruising and swelling at the injection site

The most serious side effect include infections and neutropenia but these are rare. There is a risk of hypersensitivity at 0.1-1% but severe reactions are rare.

Currently with the Covid-19 pandemic there is a potential risk if participants are infected taking anakinra. These risks are not fully known and careful judgement must be made to balance the risk of potential infection with possible benefits. Of note, Anakinra is currently used in a number of clinical trials to treat the systemic immune response to Covid-19 infection. There is no contra-indication to the current vaccines against Covid-19 for patients on anakinra as these vaccines are not live.

Mitigation of risk will be done by increased follow up and surveillence compared with standard follow up with participants on Anakinra. While these ARs are known or specifically assumed side effects of anakinra, all serious and non-serious AEs will be reported (see section 13).

Investigators will be made aware of any changes in the Summary of Product Characteristics (SmPC) but the protocol will not need to be amended unless it directly affects the conduct of the study.

This trial is categorised Type B (somewhat higher than the risk of standard medical care) as per the risk-adapted approach to clinical trials adopted by the MHRA.

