7.2 Exclusion Criteria

Any patient meeting any of the criteria listed below at baseline will be excluded from study participation:

- 1. Medical conditions that in the opinion of the study investigator would make it unsafe for participation or can adversely affect outcomes.
- 2. Co-existing pain that in the view of the study doctor may make assessment of outcomes related to refractory moderate to severe CRPS unreliable.
- 3. Ongoing relevant litigation where its conclusion is imminent during the course of the study.
- 4. Medical Contraindications to Anakinra such as moderate/severe or progressive renal impairment (CLCR < 60 ml/min or Estimated Glomerular Filtration Rate (eGFR)<60ml/min/1.73m² or end stage renal disease, including dialysis), or hepatic impairment (defined as any value of transaminases, γ-

glutamyl transpeptidase, or bilirubin greater than 2 times the upper normal limit) or hypersensitivity to anakinra or any of its excipients or to E.coli derived proteins.

- 5. Previous use of Anakinra.
- 6. Current or recent (within 6 months) use of other immunosuppressants or biologics.
- 7. Neutropenia defined as Absolute Neutrophil Count (< 1.5 x 10⁹/l).
- 8. Requirement to receive a live vaccine during the trial duration.
- 9. Active or latent Tuberculosis (TB) infection.
- 10. HIV, Hepatitis B or C carrier.
- 11. Brittle asthma.
- 12. Active malignancy or malignancy within 2 years
- 13. Ongoing alcohol or drug misuse at registration.
- 14. Psychiatric or other mental health disorder which in the opinion of the study investigator may interfere with successful study participation.
- 15. Commencing new therapy for refractory moderate to severe CRPS that may alter the outcome of the trial drug; this includes new pain management program treatment. Equally patients who have completed a pain management program within the past 3 months.
- 16. Subject is pregnant or breastfeeding.
- 17. Patients who have a spinal cord or dorsal root ganglion stimulator whose average pain is less than 6 out of 10 when the stimulator is on.

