All AEs will be actively monitored from the time of consent, however, only those which are related to study procedures will be monitored between consent and the baseline visit. In addition, assessment of AEs will be made at each clinic visit (baseline (0 day), 30, 60, 90, 120 day and all post-clinic telephone visits (last telephone visit will take place on day 180 by a delegated research staff).

Blood sampling and monitoring (not including research bloods) will be performed at screening, 30, 60, 90 and day 120.

AE reporting is detailed in section 13.

Quality of Life Assessments

QoL will be measured by the EuroQol EQ5D-5L (baseline (0 day), 30, 60, 90, 120 and 180 day).

Health Economic Assessments

No formal health economic assessment will be made but work status will be noted on the CRFs.

Special Assays or Procedures

QST is performed at baseline and day 120 (detailed in Appendix 3. Quantitative Sensory Testing).

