10.8 Sampling

10.8.1 Safety Sample Collection (Clinical Chemistry, Hepatic function and Haematology)

Please see schedule above and the INCA laboratory manual.

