13.7 Notes on Safety Event Recording

The following events must be recorded for the purposes of the trial:

- An exacerbation of a pre-existing illness
- An increase in frequency or intensity of a pre-existing episodic event/condition

- A condition (even though it may have been present prior to the start of the trial) detected after trial drug administration
- Continuous persistent disease or symptoms present at baseline (0 day) that worsens following the administration of the study/trial treatment
- Laboratory abnormalities that require clinical intervention or further investigation (unless they are associated with an already reported clinical event).
- Abnormalities in physiological testing or physical examination that require further investigation or clinical intervention
- Injury or accidents
- Pregnancy (See section 13.8 for more details)
- Weight loss of ≥4% within 4 months

Do not record:

- Medical or surgical procedures the condition which leads to the procedure is the AE
- Pre-existing disease or conditions present before treatment that do not worsen
- Situations where an untoward medical occurrence has occurred e.g. cosmetic elective surgery¹
- Overdose of medication without signs or symptoms*2
- The disease being treated or associated symptoms/signs unless more severe than expected for the participant's condition

*N.B. If overdose occurred **with** resulting signs and symptoms that meet the protocol criteria for AE/AR/SAE/SAR/SUSAR then they should be reported accordingly (see section 13.12 for more information) and the overdose highlighted to the LCTC team.

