#### 17 Study Framework

As this a feasibility phase II study, study outcomes are focused on safety/tolerability, recruitment and protocol/treatment adherence. Evaluations of further clinical/laboratory/quality of life measures are also performed to provide useful information to inform further study designs and sample size calculations. All outcomes will be summarised using appropriate summary measures.

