#### 23 Baseline Characteristics

Descriptive statistics will be reported overall. Categorical data will be summarised by frequency and percentages with the denominator as the number registered. Continuous data will be summarised by mean, standard deviation (SD), median, inter-quartile range (IQR), minimum and maximum.

Patient demographics are to be summarised as follows from Form 1:Screening:

- Age (years)
- Age categorised for EudraCT
  - Adults (18-64 years)
  - o From 65 to 84 years
  - o 85 years and over
- Sex
- o Male
- o Female
- Ethnicity
  - Arab
  - Asian Other
  - Bangladeshi
  - Black African
  - o Black Caribbean
  - Black Other
  - Chinese
  - Gypsey or Irish Traveller
  - Indian
  - o Irish
  - Other ethnic group

- Other mixed
- Other white
- Pakistani
- White and Asian
- White and Black African
- o White and Black Caribbean
- o White British
- Clinical chemistry/Hepatic functions tests\*
  - o Sodium
  - Potassium
  - o Urea
  - Creatinine
  - Biblirubin
  - o ALT
  - Alkaline Phosphatase
  - GGT
- Haematology Tests\*
  - o Full Blood count
  - o Full Blood count differential
  - Neutrophil count
  - Neutrophil count result (10^9/L)

\*All Clinical chemistry/Hepatic functions tests and Haematology Tests will be summarised with the categories Normal, Abnormal NCS and Abnormal CS as collected on the CRF (bar the Neutrophil count result which is numeric).

The below patient demographics are collected on both Form 1 Screening and Form 2 Baseline, summaries should be provided for Form 2 but if missing the value on Form 1 should be used:

Vital signs

- Height [cm]
- Weight [kg]
- Heart rate [bpm]
- Blood pressure [mmHg]

Limb volume

• Limb volume (Lower) [cm]

LCTC\_ST003\_TEMP1: SAP Template, V0.1, 08/01/2021 (developed using LCTC\_GE001\_TEMP4: LCTC Template of a Template, V1.0, 04/09/2020)

CLINICAL TRIALS CENTRE LCTC

Limb volume (upper) [cm]

Average pain score over last 24 hours:

At baseline

Research blood samples:

Consent to blood samples (Yes/No)

Blood sample taken (Yes/No)

**24** Compliance with Interventions

Exposure to treatment will be assessed by mean dose (mg) per participant. Dosing is once daily for a

maximum of 120 days; the mean and median number of doses per participant over the treatment

period (expressed as number of days treatment administered for) will be summarised.

Compliance of treatment will be captured by summarising the number of returned used syringes

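### Safety bloods are taken at four on-treatment visits, but the SAP specifies a laboratory summary at screening only, so an on-treatment neutrophil, liver or renal abnormality reaches the final report only through an investigator's action

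*SAP*

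**What the plan says.** **Collection.** Protocol 10.7 (Safety Assessments) states: "Blood sampling and monitoring (not including research bloods) will be performed at screening, 30, 60, 90 and day 120". Table 4 shows chemistry/hepatic function and haematology at those times and also marks them at premature discontinuation.

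**Why these bloods matter here.** The primary objective (protocol 5.4.1) is safety and tolerability. Protocol 5.3.1 says: "The most serious side effect include infections and neutropenia but these are rare". Exclusion criterion 7 (protocol 7.2) reads "Neutropenia defined as Absolute Neutrophil Count" below 1.5 x 10^9/L.

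**Analysis.** SAP 23, Baseline Characteristics, lists the chemistry, hepatic and haematology tests under the lead-in "Patient demographics are to be summarised as follows from Form 1:Screening". They are reported as Normal, Abnormal NCS or Abnormal CS, except for the neutrophil count, which is numeric. SAP 26 covers safety evaluations: "All non-serious adverse events (AEs) and SAEs reported by the clinical investigator will be presented". SAP 27 plans no additional analysis. SAP 17 says in general terms "Evaluations of further clinical/laboratory/quality of life measures are also" performed to inform later designs.

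**Routes by which an abnormal result can surface.** Protocol 13.1 counts an abnormal laboratory finding as a possible AE. The list of events that must be recorded in protocol 13.7 includes "Laboratory abnormalities that require clinical intervention or further investigation", unless the abnormality belongs to a clinical event already reported. Protocol 10.9 and SAP 11.3 name a newly developed exclusion criterion among the reasons for which treatment may be discontinued. SAP 19 reports treatment discontinuations with their reasons.

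**The concern.** In a trial whose first question is safety, the planned report would hold pre-treatment laboratory results and no specified on-treatment ones. The questionnaires completed at the same visits (PHQ-9, BPI, HADS) each get summaries at every visit and profile plots. The safety bloods get none after screening.

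Whether a low count or raised liver test is visible then depends on what the investigator did about it, and not on the value measured. A report of good tolerability could be issued without showing how far or when neutrophil counts fell. The designers of the later RCT would have no tabulated laboratory data from which to plan monitoring or safety endpoints.

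**Working it through.** The documents state no figure on this point, so there is none to reproduce. The check is a comparison of texts, followed by arithmetic for scale.

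**1. What is collected and what is summarised**

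| Time | Bloods taken (protocol 10.7, Table 4) | Summary specified in the SAP |
|---|---|---|
| Screening | Yes | Yes, section 23 |
| Days 30, 60, 90, 120 | Yes | None |
| Premature discontinuation | Marked in Table 4; not in the 10.9 list of data collected at discontinuation | None |

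No part of SAP 25, 26 or 27 defines an on-treatment laboratory table, a change from screening, a shift table or a count of participants crossing a threshold.

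Maximum number of on-treatment sets: 30 participants x 4 visits = 120, or fewer with discontinuation. Number with a specified final summary: 0.

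**2. When a low count would not appear**

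Take a participant whose neutrophil count falls from 4.0 to 1.4 x 10^9/L (an invented example). It appears in the final tables if either of these happens:
- It is recorded as an AE. Protocol 13.1 permits this. Protocol 13.7 requires it if intervention or further investigation is needed and the finding is not part of an event already reported.
- Treatment is stopped because an exclusion criterion is newly met, and that reason is recorded.

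It appears in no specified table if the investigator judges that no action is needed, does not choose to record an AE, and continues treatment. A low count accompanying an infection already reported as an AE also need not be recorded as a separate event.

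**3. How likely the situation is to arise**

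The documents give no rate of on-treatment counts below 1.5 x 10^9/L, so a range is assumed. The chance that at least one of 30 participants falls below it is 1 - (1 - p)^30:

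| Assumed true rate p | Chance of at least one in 30 |
|---|---|
| 1% | 26.0% |
| 2% | 45.5% |
| 5% | 78.5% |
| 10% | 95.8% |

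This is the chance that a low count occurs. It is not the chance that it is missed, which the documents do not allow one to estimate. Each participant missed would understate the proportion by 1/30 = 3.3 percentage points.

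**4. What could be stated if the counts were tabulated**

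Exact (Clopper-Pearson) two-sided 95% intervals, if all 30 have on-treatment counts:
- 0/30: 0% (0 to 11.6%); the upper limit is 1 - 0.025^(1/30) = 0.116
- 1/30: 3.3% (0.1 to 17.2%)
- 2/30: 6.7% (0.8 to 22.1%)

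With m participants measured and none low, the upper limit is 1 - 0.025^(1/m), which widens as m falls.

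**The case against.** The strongest reply is that the gap is narrower than the missing table suggests. Protocol 13.7 sets a list that must be recorded, and does not say that nothing else may be. Protocol 13.1 explicitly allows an abnormal laboratory finding to be an AE. A repeat count prompted by a low result could itself be further investigation. A count below 1.5 x 10^9/L meets an exclusion criterion, which gives a second route through discontinuation. The IDSMC receives safety data at least annually (SAP 18.1.3 and 25.1.1), and SAP 6 allows analyses outside the plan if they are justified.

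All of this is correct, and it rules out several stronger readings that a reader might infer:
- That a low count will go unreported. Two routes exist; it can go unreported, no more.
- That the primary result is affected. The primary outcome counts only serious and condition-specific (pain) events, so a non-serious laboratory change lies outside it.
- That SAP 17 contradicts SAP 26 and 27. Its sentence names no test, time or table. It is a general statement with nothing specified behind it.
- That nobody will look at the bloods. Laboratory content is neither specified for nor excluded from the IDSMC reports.
- That these are the only objective safety markers. Heart rate, blood pressure and weight are also scheduled at clinic visits, and weight loss of at least 4% within 4 months is a recordable event.

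The central point stands. Both routes depend on an investigator's decision, the IDSMC reports are not the final report, and a laboratory table added later under SAP 6 would be an unplanned analysis needing justification.

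**Conclusion.** The point holds as an omission of supporting safety tables that should be corrected. Followed exactly, the SAP yields a final report with no specified summary of up to 120 on-treatment blood sets, in a trial whose primary objective is safety and whose protocol names neutropenia among the most serious known effects. An abnormality that the investigator neither records as an AE nor acts on by stopping treatment can be absent from it.

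The number of abnormalities that would be lost cannot be estimated from the documents. The 120 assumes that all 30 participants attend all four visits. The 11.6% limit assumes that all 30 have on-treatment counts. The value 1.5 x 10^9/L is the trial's eligibility cut-off, used here only as a reporting threshold.

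**What to change.** First confirm that the follow-up forms hold the numeric neutrophil count and the Normal / Abnormal NCS / Abnormal CS categories. The SAP describes these formats only for the screening form.

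Then add to SAP 26, on the safety set already defined in SAP 22.2:
- Neutrophil count, value and change from screening, at days 30, 60, 90 and 120, and at discontinuation where a sample was drawn.
- Each participant's lowest on-treatment count, and the number and percentage ever below 1.5 x 10^9/L with an exact 95% interval. The denominator is participants with at least one on-treatment count.
- Shift tables from the screening category to the worst on-treatment category for the chemistry, hepatic and haematology tests.

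Counts against the protocol's other eligibility limits (liver tests above 2 times the upper normal limit, eGFR or CLCR below 60) should be added only if numeric values are held. SAP 23 lists the liver tests by category and does not list eGFR or CLCR.

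The cost is SAP wording, a few tables and the check of the forms. It needs no new samples or visits, and it sets no clinical rule.
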